In addition to evaluating the effects of NAC, the proposed Phase II proof-of-concept study is designed to gather key data to inform future Phase III treatment efficacy trials for adolescent AUD, including effect size estimates. There is no currently established template for adolescent AUD pharmacotherapy trials. While adult trials may be informative, adolescents with AUD often differ from adults in alcohol use patterns, use-associated problems, and receptiveness to, as well as adherence with, treatment. Before proceeding to a Phase III efficacy trial in adolescents, a number of developmentally-informed methods must be embedded and evaluated for feasibility and value in a proof-of-concept trial. In addition to traditional, established, office-based clinical trial procedures, we propose utilizing mobile technology to improve data collection, engagement, and medication adherence. We additionally propose comparing the value of a cross-section of self-report and biological measures of alcohol use and related behaviors, to determine the most appropriate measures for inclusion as efficacy outcomes in Phase III trials.

With these methodological considerations in mind, and in response to National Institute on Alcohol Abuse and Alcoholism (NIAAA) RFA-AA-18-009 *Medications Development for the Treatment of Alcohol Use Disorder*, we propose preliminarily testing the effects of NAC, compared to placebo, on a platform of weekly evidence-based brief alcohol intervention for adolescents with AUD (*N*=120). We will (1) conduct an 8-week, intent-to-treat, double-blind, parallel-group, randomized, placebo-controlled trial of NAC (2400 mg per day); (2) examine standardized, repeated dependent measures of clinical outcomes at baseline, throughout treatment, and at post-treatment follow-up; and (3) employ mobile technology to improve data collection, engagement, and medication adherence. The following specific aims are proposed:

Specific Aim 1. To evaluate the effect of NAC, as compared to placebo, in reducing alcohol use (total standard drinks) among treatment-seeking adolescents with AUD.

Specific Aim 2. To evaluate the feasibility and utility of implementing developmentally-informed methods, including those that leverage mobile technology, to conduct a randomized, placebo-controlled trial of a pharmacotherapy for adolescent AUD.

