Remote Visits – The informed consent/assent procedure can be conducted remotely via REDCap and Zoom. Participants will complete direct-entry REDCap surveys remotely. The study medical clinician will have the option to conduct assessments and cessation counseling remotely via Zoom or phone. All visits taking place can be conducted entirely remotely via REDCap, Zoom, or phone. Participants may receive study medication by mail. The participant will also be provided supplies required to complete an offsite/at home urine collection and CLIA waived qualitative EtG test, UDS, and pregnancy test for participants assigned female at birth, the results of which will be verified using video and photo capture. The alcohol breathalyzer test and the blood draw will not occur during remote visits.

In addition, a hybrid model can be utilized if an in-person participant has an unexpected conflict with attending an in-person visit (e.g., transportation issue or travel), arrangements may be made to remotely complete visit procedures, in order to maintain data collection and study engagement. In very rare instances, study medication may be shipped to a participant when extended or indefinite relocation from the study center would prevent regularly planned medication management (dispensing/accountability and compliance) at an in-clinic visit. For remote or hybrid participants medications will be shipped in proper packing with tracking to protect medication as well as participant privacy. Prior to the mailing of any materials, ongoing participant interest in continued study participation will be confirmed, dosing instructions and safety needs will be reviewed, and depending on the ability to physically return study medication/blister packs, appropriate destruction measures will be provided. If such remote measures are employed, participants will be directed to have more extended visualization of their medication blister packs in their video recording of study medication dosing to allow study personnel to properly monitor medication accountability.

In our prior NAC trial for CUD, with the above-mentioned strategies in place, among participants presenting for any visits after medication initiation, 84% completed the entire course of treatment. We maintain similar success in our ongoing studies focused on adolescent tobacco (U01DA031779), cannabis (R01DA042114), and alcohol (K23AA025399) use disorders.

Instruments/Measures/Materials (see Study Timetable for an overall summary)

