12.0 Data Management

Statistical Methods

Power and Sample Size

This Phase II proof-of-concept trial is powered on the primary hypothesis that there will be a clinically significant differential in the decrease in total standard alcohol drinks and drinks per drinking day during the final four weeks of treatment (weeks 5-8) in the NAC group compared to the placebo group. In the proposed study, the two treatment arms, NAC and placebo, will be assessed for differences in drinking behavior using general linear models. In a prior pilot trial assessing adolescent drinking behavior (N=11), our team noted an average total of 49 (SD=26) drinks with 5.5 (2.0) drinks per drinking day during the 4 weeks prior to study enrollment. Additionally, although the participants noted in our prior CUD trial were not required to exhibit AUD nor was treatment targeted at drinking behavior, the heavier drinkers in the study (upper quartile of total drinks prior to baseline, ≥ 24 drinks/30 days) reported a mean of 58 (SD=30; median=54 drinks) drinks during the 4 weeks prior to study entry.²⁶ In this sample of heavier drinkers, those randomized to placebo had a median 10.7% decrease in total drinks at the end of CUD treatment (last 4 weeks of study treatment) as compared to a median 33.0% decrease in total drinks in the NAC treated group. Assuming a more robust treatment effect when alcohol use is the therapeutic target, a 50% decrease in total drinks during the final 4 weeks of study treatment in the active treatment group, as compared to baseline, would be a clinically relevant treatment effect. We conservatively estimate a similarly more robust 20% decrease in total drinks in the placebo treated group. Assuming similar baseline drinking behavior to the adolescent study (baseline mean=49 drinks/4 weeks) and a similar group level variance estimate as in the baseline study data (SD=25), we will have 80% power with a 5% type I error rate to detect the clinically relevant difference between a 50% decrease in the NAC treated group and 20% decrease in the placebo treated group (equivalent to 25 total drinks versus 40 total drinks during the final 4 weeks of treatment) with 45 participants randomized to each treatment group (n=90 total). Additionally, we anticipate that retention may be a challenge in this population, and we anticipate a 25% drop-out rate during study treatment, inflating the necessary randomized sample size to n=60 participants per treatment arm (N=120total randomized participants). The noted sample will have greater than 90% power to find a

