
Version: 16; Version Date: 11JULY2023

corresponding 50% decrease in drinks per drinking day in the NAC treated group as compared to a 20% decrease in the placebo treated group [2.8 (SD=2.0) vs. 4.4 (2.0) drinks per drinking day].

Primary Data Analysis

Baseline clinical and demographic characteristics will be collected and contrasts of baseline characteristics and clinical predictors of substance use will be performed between groups. Continuous and ordinal characteristics will be compared using a Wilcoxon Rank-Sum test statistic while categorical characteristics will be compared using a Pearson Chi-Square test statistic. If a baseline characteristic is significantly associated with the outcomes of interest, the corresponding variables will be used as initial covariates in the model analyses. Secondarily, possible covariates will be tested for confounding effects on the models specified and when present, they will be included in the final adjusted model. Specific Aim 1: The primary measure of interest will be the estimated reduction in self-reported standard alcohol drinks and the associated variance around these estimates during the final four weeks of study treatment (weeks 5-8) in those randomized to NAC as compared to those randomized to placebo. The main effect of NAC versus placebo on the total number of standard drinks will be assessed using generalized linear models and modelbased means with associated standard errors will be reported. Analytic models will be computed both unadjusted and adjusted for significant covariates and confounders found in the preliminary analysis. Specific Aim 2: Self-reported drinking (weekly TLFB and mobile technology-delivered daily diary) as well as biomarkers of recent alcohol use (EtG, CDT, PEth, and alcohol breathalyzer) will be collected at study visits. Agreement between collection measures will be measured as percent agreement and kappa coefficients. Agreement will be assessed weekly during the entire time course of the treatment study and deviations between self-reported moderate/heavy use and biomarker-indicated moderate/heavy use will be assessed to characterize the reporting (under-reporting) of self-reported use amounts. Similarly, medication adherence will be measured at weekly study visits using self-report (self-report and mobile technology delivered video) and MEMS. Concordance percentages and kappa coefficients will be calculated between the adherence measurement methods. Due to high prevalence of self-reported adherence in substance use disorder studies, kappa coefficients will be calculated as the prevalence adjusted bias adjusted kappa (PABAK).⁶² Clustered logistic regression model using the methods of generalized estimating equations will be applied to assess the differences in self-reported drinking and medication adherence measurement methods on binary adherence outcomes over time.⁶³ Working correlation structures will be independently compared and the final model structures will be chosen using the quasilikelihood under the independence model criterion statistic.⁶⁴ The main effects of measurement method and visit, as well as the interaction between method and visit, will examined for significance.

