
All randomized participants will be included in the primary analysis (intent-to-treat; ITT) and all statistical models will be implemented using SAS v. 9.4.

Secondary Data Analysis

In addition to the primary use outcome, secondary models will assess overall alcohol abstinence, the proportion of drinking days and the proportion of heavy drinking days noted during the final 4 weeks of study treatment. The temporal pattern in weekly drinking behavior over the course of the entire study is also of interest. Weekly drinking data in this population is likely to follow a Poisson distribution and will be assessed using random effects Poisson/Negative Binomial models and in the case of a high number of participants achieving abstinence from weekly alcohol use, zero inflated models will be explored. Similarly, binary weekly abstinence data will be assessed using mixed effects logistic regression models to assess the log-odds of weekly abstinence in the NAC- versus-placebo treated participants. Durability of treatment effects will be assessed through analysis of post-treatment alcohol use data at the Week 12 and Week 26 post-treatment visits, using model development processes similar to Specific Aim 1.

To assess the association between alcohol use reduction and changes in functional outcomes (alcoholrelated problems; alcohol craving; cognitive task performance; anxiety, mood, and sleep quality measures; quality of life), general linear regression models will be developed. Outcome specific distributions will be used to model functional and cognitive outcomes (e.g., count, binary and Gaussian). For Gaussian distribution assumptions, residual normality will be assessed using QQ plots, and when deviations from normality occur appropriate transformations will be made.

Missing Data and Attrition

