Missing data are common in longitudinal alcohol clinical trials where use rates are the primary end point. The primary cause attributed to such missing data is participant attrition. Attrition can introduce bias into the parameter estimate and reduce study power, estimate precision and generalizability. In order to minimize missing data and study attrition, study simplification and enhanced communication between study coordinators and participants will be emphasized. We will make every effort to prevent attrition, e.g., phone/text/email reminders prior to visits, compensation for participation, meeting with participants in community if needed, and reinforcing adherence at each visit. However, these methods do not ensure that all data will be collected and appropriate analysis methods will be employed to accommodate missing data. Simply replacing missing data with the last observation carried forward or using worst case scenario adds substantial bias to both parameter and variance estimates.65,66 Maximum likelihood methods (ML) yield valid inferences assuming ignorable attrition (i.e., attrition is accounted for by covariates or the dependent variable measured prior to dropout). Additionally, Full Information Maximum Likelihood methods (FIML) will be implemented and compared to the results from the ML estimation to assess bias that may be present due to missing data.⁶⁷ In addition, in keeping with the Intent to Treat Principle, we will make every effort to continue assessments for the entire course of randomized treatment, even among those who fail to adhere to randomized assignment or stop participating in the study assigned intervention.

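### The only planned check for missing-data bias compares FIML with ML; both assume ignorable attrition, so agreement cannot show that the weeks 5–8 drink total is free of dropout bias

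*Combined protocol and SAP*

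**What the plan says.** All of the following is in the combined protocol and SAP.

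- **Primary analysis (12.0, Primary Data Analysis, Specific Aim 1).** "The main effect of NAC versus placebo on the total number of standard drinks will be assessed using generalized linear models". The outcome window is weeks 5–8, and everyone randomized is to be analysed.
- **Missing data (12.0, Missing Data and Attrition).** The section argues against last observation carried forward and worst-case replacement. It then states: "Maximum likelihood methods (ML) yield valid inferences assuming ignorable attrition". The single step offered for assessing missing-data bias is: "Full Information Maximum Likelihood methods (FIML) will be implemented and compared to the results from the ML estimation to assess bias". Neither fit is specified further.
- **Weekly drinking (12.0, Secondary Data Analysis).** The pattern over time "will be assessed using random effects Poisson/Negative Binomial models".
- **Expected loss (12.0, Power and Sample Size).** "we anticipate a 25% drop-out rate during study treatment".
- **Earlier experience (10.0, Remote Visits).** In the team's previous NAC trial, "among participants presenting for any visits after medication initiation, 84% completed the entire course of treatment".
- **Limiting missing data.** Section 12.0 says "we will make every effort to continue assessments for the entire course of randomized treatment", including for participants who stop the intervention. Section 10.0 allows remote visits and uses Timeline Follow-Back (TLFB) interviews to fill gaps in the daily reports.
- **Use of the result (1.0).** The trial is meant to "gather key data to inform future Phase III treatment efficacy trials for adolescent AUD, including effect size estimates".

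**The concern.** A check on an assumption should be able to give a different answer when the assumption fails. FIML and ML are both likelihood methods, and both are valid only if attrition is ignorable. They can differ when FIML uses observed data, such as weeks 1–4, that the ML fit leaves out. That difference shows what the extra observed data do to the estimate. It says little or nothing about drinking that changed after contact was lost and that earlier data do not predict.

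The weekly random-effects models do not fill the gap, because they use partial data under the same assumption. Continued assessment, remote visits and TLFB back-filling reduce the amount of missing data but do not test the assumption for what stays missing. No analysis in section 12.0 departs from ignorability.

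The trial is to supply effect sizes for Phase III, so the size of the estimate matters as well as its significance. As planned, the report could not show how far that size depends on what dropouts drank.

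**Working it through.** **1. The plan's own figure.** Inputs from Power and Sample Size: baseline 49 drinks per 4 weeks, 50% and 20% decreases, SD 25, 5% type I error (taken as two-sided), 80% power.

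- Means: 49 × 0.5 = 24.5 and 49 × 0.8 = 39.2. The difference is 14.7; the plan rounds to 25 versus 40, a difference of 15.
- n per arm = 2 × (1.960 + 0.842)² × 25² / 15² = 43.6, so 44. With 14.7 it is 45.4, so 46. The plan states 45.
- Inflation: 45 / (1 − 0.25) = 60 per arm. The sample size is reproduced, and nothing below changes it.

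**2. How much could dropouts' drinking move the estimate?** Let p be the share in each arm without weeks 5–8 data, and dP and dN the mean drinks of those participants in the placebo and NAC arms:

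difference = [(1 − p) × 39.2 + p × dP] − [(1 − p) × 24.5 + p × dN]

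The documents give neither p nor dP and dN for this purpose, so these are assumptions. I use p = 25% (the plan's dropout figure), 16% (100% − 84% from the earlier trial, which leaves out people never seen after starting medication) and 10% (not every dropout need lack the data). P-values use the completer standard error, 25 × √(2/n), with n = 60 × (1 − p).

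| | p = 25% | p = 16% | p = 10% |
|---|---|---|---|
| n per arm; SE | 45; 5.27 | 50.4; 4.98 | 54; 4.81 |
| Both arms return to 49 | 11.0 (p=0.039) | 12.3 (p=0.015) | 13.2 (p=0.007) |
| NAC only returns to 49 | 8.6 (p=0.11) | 10.8 (p=0.03) | 12.3 (p=0.01) |
| Placebo only returns to 49 | 17.2 | 16.3 | 15.7 |
| +10 drinks in both arms | 14.7 | 14.7 | 14.7 |

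Example: NAC only at 25% gives 39.2 − (0.75 × 24.5 + 0.25 × 49) = 39.2 − 30.6 = 8.6.

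**3. NAC-only tipping shift.** This is delta = (14.7 − critical difference) / p.

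- 25%: (14.7 − 10.47) / 0.25 = 16.9, a NAC dropout mean of about 41, below the baseline of 49.
- 16%: (14.7 − 9.88) / 0.16 = 30.1, a mean of about 55, above baseline.
- 10%: (14.7 − 9.54) / 0.10 = 51.6, a mean of about 76, well above baseline.

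A cross-check by multiple imputation with Rubin's rules (60 per arm, predictors baseline and weeks 1–4) gives similar values. With 15 missing per arm, p = 0.048 at a shift of 18 and 0.061 at 20. With 10 missing per arm, p = 0.045 at 27 and 0.056 at 30.

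**4. What would the FIML–ML comparison show?** This is a simulation with 300,000 per arm, gamma totals with SD 25 and 25% missing. FIML uses baseline and weeks 1–4; ML does not use weeks 1–4. Assumed weeks 1–4 means are 32 and 42, and assumed latent correlations between periods are 0.6, 0.5 and 0.7.

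| Dropout mechanism | ML | FIML | Truth |
|---|---|---|---|
| NAC dropout depends on weeks 1–4 | 18.65 | 14.66 | 14.69 |
| NAC dropout depends on own weeks 5–8 | 20.80 | 18.81 | 14.71 |
| Random dropout, then return to own baseline, both arms | 14.67 | 14.69 | 10.95 |
| The same, placebo only | 14.76 | 14.76 | 17.23 |

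In the first row the check works. In the second it flags a problem, but FIML is still about 4 drinks off. In the last two the fits agree and the bias is hidden, once in each direction.

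A smaller simulation (60 per arm, true difference 15, correlation 0.5, ML adjusted for baseline) also let NAC dropout depend on weeks 5–8 drinking. It gave ML 20.1 and FIML 19.5 against a full-data 14.9. The fits were about half a drink apart while both were about 5 drinks off.

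**The case against.** - **The plan does not say that agreement would rule out bias.** It says only that the comparison will assess bias. That stands: a reader might infer a claim of proof, but the text makes none. The point is that no other check is planned and the limits of this one are not stated.
- **The comparison is not worthless.** A reader might infer that it can never detect non-ignorable dropout. Step 4 shows otherwise: it can diverge, and by how much depends on what each fit contains, which the plan leaves open. The fully hidden cases require dropout that earlier data do not predict.
- **Missingness may be well below 25%.** That figure is dropout during treatment, not absence of weeks 5–8 data. Assessment continues after the intervention stops, visits can be remote, and the study timetable schedules TLFB-confirmed reports again at Weeks 12 and 26. This also stands, and at 10% missing the verdict is robust.
- **This is a Phase II proof-of-concept trial.** True, but its stated purpose includes effect sizes for Phase III.
- **The missed-visit rule might count as a second analysis.** Retention Strategies (10.0) describes the intent-to-treat analysis as treating each missed visit as one with drinking. That can code a binary abstinence outcome. It supplies no drink count and is not offered as a bias check.

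**Conclusion.** The concern holds in limited form. The one planned check shares the assumption it would need to test, so FIML–ML agreement cannot show that the weeks 5–8 total is free of dropout bias.

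On the plan's figures and the assumed scenarios, the 14.7-drink difference could be 8.6 to 17.2 at 25% missing, 10.8 to 16.3 at 16%, and 12.3 to 15.7 at 10%. Significance is lost in only one of these cases, NAC-only return to baseline at 25% missing. Equal dropout with equal shifts produces no bias.

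Three stronger readings are not supported:

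- **That the primary model is wrong or the result will be biased.** Nothing in the documents shows that attrition will be non-ignorable, and the bias could run either way.
- **That only the size is at risk, or that the verdict is generally at risk.** Both depend on the scenario: the first holds when both arms return to baseline, the second needs a NAC-specific shift and high missingness.
- **That a Phase III trial sized on this estimate would be underpowered by a known amount.** That would assume that Phase III observes every dropout's drinking with SD 25, which the documents do not say.

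**What to change.** In section 12.0, Missing Data and Attrition, keep the FIML–ML comparison and add:

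1. One pre-specified delta-adjusted (tipping-point) multiple-imputation sensitivity analysis of the primary weeks 5–8 total, with delta allowed to differ by arm. Report return to baseline as one case within it, so that it is not a single-value replacement of the kind the section argues against. Impute from baseline and all observed weeks 1–8 drinking, and impute only the missing part of a partly observed total.
2. A sentence saying that FIML–ML agreement alone will not be read as absence of missing-data bias.

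The primary generalized linear model for Specific Aim 1 stays as it is.

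The cost is SAP wording and a little programming, with no new data or participants. The result may look less robust. The team ran a multi-method missing-data analysis in its earlier adolescent cannabis trial (2.0, Preliminary Studies), though post hoc and on a binary outcome.

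As a separate matter, reconcile the missed-visit statement in Retention Strategies (10.0) with the rejection of worst-case replacement in 12.0, for example by limiting the former to binary abstinence outcomes.
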